16. DATA AND SAFETY MONITORING PLAN

Only trained research assistants at UCH-Memorial will be responsible for consent of subjects, with support of the site-PI, site-sub-I and/or PI as needed (see consent section for details). The research assistants at UCH-Memorial will be responsible for completion of patient assessments and reporting of potential safety issues and/or protocol violations to the site-PI, site-sub-I and PI. In addition, the PI will review data assessments uploaded to REDCap monthly for completion. Site screening/enrollment logs will be reviewed monthly. Study personnel at both sites will undergo an initial training by the PI at onset of study which will include review of the study protocol, inclusion/exclusion criteria, the consent process, methods of sample collection and processing, patient assessments, and standardized chart review methods. The trained research assistants at both sites will have complete required human subjects research trainings and specific training to ensure accuracy of the NIHSS scoring prior to completing these assessments on any subjects. A standard operating procedures (SOP) manual will also be provided for references. Training will be refreshed annually or sooner if there are protocol changes and/or any compliance concerns.

Safety oversight will be under the direction of a Safety Monitoring Committee (SMC), composed of individuals with the appropriate expertise, including stroke, neurocritical care, and emergency medicine. Members of the SMC will include members of the investigative team. However, measures will be in place to minimize perceived conflict of interest. The SMC will meet at least semiannually to assess safety and efficacy data on each arm of the study.

Assessment of safety measures and adverse events:

Study personnel and the subject's treating physician will regularly monitor subjects for safety measures and adverse events. This includes practices that are associated with routine patient care (i.e. vital sign assessments, assessment of neurologic deterioration, development of respiratory compromise). Specific monitoring includes the following:

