4. Development of respiratory compromise – While patients are continuously assessed by their treating medical team, study personnel will specifically assess study subjects at the T0+4hour and T0+24hour evaluations for worsening respiratory status and the need for additional supplemental oxygen. At the final 3-month assessment, patients' medical records will also be reviewed for evidence of respiratory deterioration while the patient was hospitalized and up to this final assessment including: need for additional supplemental oxygen, need for non-invasive positive pressure ventilation, mechanical ventilation, development of pulmonary edema, development of pneumonia.
5. Development of post-stroke infections – Neuroinflammation after a stroke also results in immunosuppression. As such, this places patients at increased risk of post-stroke infections, the two most common being pneumonia and urinary tract infections which may account for up to 30% of deaths after an AIS⁶⁰. Additionally, there may be sex-based differences in post-stroke infections that could be related to underlying hormone status⁶¹. As such, patients will be screened at the 3-month assessment to determine if they experienced any post-stroke hospitalizations and/or treatment for pneumonia, urinary tract infections, sepsis, or other infections. In addition to asking subjects directly at this assessment, their medical record will also be reviewed for re-admissions while it is being reviewed for the above respiratory compromise.

Definition and Classification of Adverse Events: An adverse event means any untoward medical occurrence, unintended sign, symptom, or disease temporarily associated with the use of an intervention in humans, whether or not considered intervention-related. All AEs will be documented and analyzed further. Subjects will be monitored for signs of an AE at T0+4hr and T0+24hours.

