An adverse event (AE) or suspected adverse reaction is considered "serious" if it results in any of the following outcomes: death, a life-threatening adverse event, prolongation of existing hospitalization, a persistent or significant incapacity or substantial disruption of the ability to conduct normal life functions. Important medical events that may not result in death, be life-threatening, or require hospitalization may be considered serious when, based upon appropriate medical judgment, they may jeopardize the participant and may require medical or surgical intervention to prevent one of the outcomes listed in this definition.

For adverse events (AEs), the following guidelines will be used to describe severity.

- **Mild** – Events require minimal or no treatment and do not interfere with the participant's daily activities.
- **Moderate** – Events result in a low level of inconvenience or concern with the therapeutic measures. Moderate events may cause some interference with functioning and/or the need for further supplemental oxygen or antibiotic treatment.
- **Severe** – Events interrupt a participant's usual daily activity and may require systemic drug therapy or other treatment. Severe events may include need for mechanical ventilation, vasoactive infusion, are usually considered potentially life-threatening or incapacitating.

The PI will be responsible for determining whether an adverse event (AE) is expected or unexpected. An AE will be considered unexpected if the nature, severity, or frequency of the event is not consistent with the risk information previously described for the study intervention.

The following AEs are considered to be expected:

1. Bleeding and/or hematoma formation at sight of arterial puncture
2. Pain at the sight of arterial puncture lasting after collection of ABG
3. Hemorrhagic conversion in up to ~40% of study subjects

The occurrence of an adverse event (AE) or serious adverse event (SAE) may come to the attention of study personnel during study observation time points or upon review by a study monitor.

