All AEs including local and systemic reactions not meeting the criteria for SAEs will be captured on the appropriate case report form (CRF). Information to be collected includes event description, time of onset, clinician's assessment of severity, relationship to study intervention (assessed only by those with the training and authority to make a diagnosis), and time of resolution/stabilization of the event. All AEs occurring while on study must be documented appropriately regardless of relationship. All AEs will be followed to adequate resolution.

Any medical condition that is present at the time that the participant is screened will be considered as medical history and not reported as an AE. However, if the study participant's condition deteriorates at any time during the study, it will be recorded as an AE.

Changes in the severity of an AE will be documented to allow an assessment of the duration of the event at each level of severity to be performed. AEs characterized as intermittent require documentation of onset and duration of each episode.

The study PI will record all reportable events into a database with start dates occurring any time after randomization until completion of the study. At T0+24hours, study personnel will inquire about the occurrence of AE/SAEs since the last observation point. Solicited and unsolicited events will be captured. Unsolicited AEs will be identified by asking participants if they "have noticed anything different since beginning the treatment after the onset of your stroke." Solicited AEs will include: 1) any trouble breathing, 2) development of pneumonia, 3) need for additional oxygen therapy, 4) hemorrhagic conversion of the stroke. Events will be followed for outcome information until resolution or study completion.

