17. DATA ANALYSIS PLAN

The primary endpoint of this study is feasibility. We hypothesize that the challenges of enrolling and randomizing AIS patients to a therapeutic intervention within less than one hour of ED presentation can be addressed. The number of potential subjects meeting the inclusion criteria and the relative rates of enrollment over time will be tracked. Additionally, the timing to enrollment and initiation of treatment intervention will be monitored. The primary endpoint of this study is feasibility as measured by the mean time from presentation to the ED to randomization and initiation of intervention. We hypothesize that we will be able to enroll, randomize and initiate treatment intervention in less than one hour for 80% of the enrolled subjects.

This study is not powered to detect significant differences in secondary or exploratory outcomes. However, analysis of secondary outcomes will occur both on an intention-to-treat and a per-protocol basis. Penumbral salvage will be reported as an average and as a standard deviation of the mean. We plan to enroll a total of 200 patients. Based on previous data that showed a decrease in the relative infarct volume growth (infarct volume at presentation/infarct volume at 4 hours) in patients treated with hyperoxia (87.8 +/-22%) compared to controls (149.1 +/- 41%)²⁹, 5 patients per arm would be needed to detect a similar difference with a power of 90% and type I error rate (α) of 0.05⁶². However, this effect was seen in a small study with less than 10 patients per treatment arm. Thus, such dramatic changes in infarct volume may not be expected, but even a smaller reduction in infarct volume will be clinically important as small reductions in infarct volume can have profound clinical effects if it is in a key cerebral territory. If you assume 20% of patients for some reason do not receive standard follow-up imaging to allow for calculation of infarct progression, a standard deviation of 41%, 80% power and α of 0.05, the proposed sample size will be able to detect an absolute difference in infarct volume growth of 18% between the control and hyperoxia.

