In terms of effects on clinical patient outcomes, both the effect on 3-month mRS and NIHSS will be determined. The DEFUSE-3 study found the median NIHSS score in AIS patients evaluated for possible extended-window thrombectomy was 16 with an interquartile range of 10-20⁶³. Based on these results and our proposed sample size for feasibility and a 29% loss to follow-up, we will be able to detect a two-point difference in NIHSS between the hyperoxia and control groups at 24hours with 80% power and a type I error (α) of 0.05. Given the large potential number of confounding events between the time of study intervention and a 3-month mRS, this will be analyzed on an exploratory basis. The average 3-month mRS in both the hyperoxia and control groups will be compared. Finally, an exploratory analysis of the effects of hyperoxia on biomarkers of stroke severity and hyperoxic lung injury will be evaluated over time. The change in level of biomarkers (MMP-9, IL-6, and IL-8) over time will be analyzed and reported using the mean and standard deviation and will be depicted graphically.

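### Section 17 names no baseline-adjusted between-arm analysis of NIHSS, mRS or biomarkers, and deaths enter the final analysis only through the mean 3-month mRS

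*Combined protocol and SAP*

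**What the plan says.** On function, Section 17 states that "The average 3-month mRS in both the hyperoxia and control groups will be compared" and labels this exploratory. For NIHSS it gives a power statement for a two-point difference between arms at 24 hours, whereas Section 4 lists the secondary outcome as the change over the first 24 hours. For MMP-9, IL-6 and IL-8 it promises an exploratory look at the effects of hyperoxia, and the only stated output is change over time as mean and SD with a graph. No covariate or model is named. It also says: "This study is not powered to detect significant differences in secondary or exploratory outcomes".

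The baseline values exist. Section 7 (Functional Outcomes) takes a historical mRS, Section 4 takes the initial NIHSS from the stroke consult note, and Table 1 schedules a serum sample at T0.

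Section 17 does not mention deaths, but other sections capture them. In Section 16 an event is serious "if it results in any of the following outcomes: death, a life-threatening adverse event". The same section has reportable events entered "with start dates occurring any time after randomization until completion of the study". The mRS in Section 7 runs from 0 to 6, with 6 for death. Section 16 adds: "The SMC will meet at least semiannually to assess safety and efficacy data on each arm of the study". It also says "All AEs will be documented and analyzed further", without naming an analysis. At 3 months, "medical records will also be reviewed for evidence of respiratory deterioration while the patient was hospitalized and up to this final assessment" and "patients will be screened at the 3-month assessment to determine if they experienced any post-stroke hospitalizations"; death is not listed in either of those two reviews.

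**The concern.** The secondary and exploratory outcomes are there to inform a later trial, so their value lies in the estimates and intervals they yield. Three things are left unsaid.

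- **Baseline.** NIHSS, mRS and biomarker levels after treatment are likely to depend on their starting values. Leaving collected baselines out of the comparison gives up precision.
- **Biomarkers.** Section 4 hypothesises that hyperoxia does not raise injury markers. A mean and SD of change does not by itself give the between-arm estimate and interval on which that hypothesis would be judged.
- **Deaths.** An average mRS can stay level while deaths differ, if survivors in the arm with more deaths do better. Section 4 makes preliminary data on adverse effects a study aim, and Section 8 cites a hyperoxia trial stopped early for safety, so deaths merit a line of their own.

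**Working it through.** **1. The plan's own NIHSS figure.** Inputs from Section 17: 200 patients (100 per arm), 29% loss (71 per arm), 80% power, alpha 0.05 (two-sided assumed), and an IQR of 10 to 20 from the cited thrombectomy cohort. Under normality SD = 10/1.349 = 7.41. The detectable difference is (1.960 + 0.842) × SD × √(2/71) = 0.470 × SD = 3.49 points, against the stated 2. Two points would need an SD of about 4.25, or ANCOVA at SD 7.41 with a correlation of about 0.82. The plan gives neither an SD nor a correlation. I use this only to set the scale; the present point does not rest on that figure.

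**2. Gain from adjusting NIHSS.** With correlation r between baseline and 24-hour scores and equal SDs, the variances are σ² for the 24-hour value, 2(1 − r)σ² for the change and (1 − r²)σ² for ANCOVA. So ANCOVA/change = (1 + r)/2 and ANCOVA/24-hour value = 1 − r².

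| r (assumed) | ANCOVA ÷ change | ANCOVA ÷ 24-h value | Gain vs change, points, at SD 4 / 5 / 7.4 |
|---|---|---|---|
| 0.5 | 0.75 | 0.75 | 0.25 / 0.31 / 0.47 |
| 0.7 | 0.85 | 0.51 | 0.11 / 0.14 / 0.21 |
| 0.8 | 0.90 | 0.36 | 0.06 / 0.08 / 0.11 |

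The last column is the fall in detectable difference at 71 per arm. For example, at SD 5 and r = 0.5: 0.470 × 5 × (√1 − √0.75) = 0.31. The comparison with change is the relevant one if the Section 4 definition governs; the comparison with the 24-hour value applies only if the Section 17 wording does.

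**3. Biomarkers.** The documents give no spread, skewness or correlation, so the gain cannot be sized from them. As a purely assumed illustration (1.5-fold effect, 71 per arm, correlations 0.3 to 0.7, lognormal simulation), power for raw change against log-scale ANCOVA is 24–40% against 55–80% at a log-SD of 1.2, and 63–89% against 88–99% at 0.8. At a log-SD of 0.4 every method has at least 99.9%. The benefit runs from nil to substantial, depending on skewness.

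**4. Can a mean mRS hide deaths?** Two invented sets of 100 patients, scores 0 to 6:

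- 10, 20, 20, 20, 15, 10, 5: sum 20 + 40 + 60 + 60 + 50 + 30 = 260, mean 2.60, 5 deaths.
- 18, 22, 16, 13, 3, 13, 15: sum 22 + 32 + 39 + 12 + 65 + 90 = 260, mean 2.60, 15 deaths.

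So it can; this shows possibility, not likelihood.

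**5. Precision of a death comparison.** For equal proportions p with Wilson limits l and u, the Newcombe half-width is √[(p − l)² + (u − p)²]. For 10/100 per arm, l = 0.0552 and u = 0.1744, giving √(0.0448² + 0.0744²) = 0.087. For 5, 10 and 15 deaths per 100 the half-widths are 6.8, 8.7 and 10.1 points. If only 71 per arm were evaluable (the plan's NIHSS loss, borrowed here as an assumption), 4, 7 and 11 deaths give 8.7, 10.4 and 12.1.

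**6. The cited trial.** Section 8 reports 16/43 against 6/41 deaths judged unrelated to therapy: 37.2% − 14.6% = 22.6 points (Newcombe 95% CI 3.7 to 39.4). Adding the one possibly related death per group, 17/43 against 7/41, gives 22.5 points (3.1 to 39.6).

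**The case against.** The case against is substantial. This is a feasibility study that disclaims power for these outcomes. Comparing randomised arms without adjustment is unbiased, and the plan neither promises nor rules out adjustment. The Section 4 NIHSS outcome already uses baseline as a change score, so the further gain is below half a point throughout the table, and its top value needs both r = 0.5 and an SD from a different population. Biomarker change means and SDs, if given by arm, let a reader compute a contrast. All of this stands, and it is why the matter is an improvement and not a fault.

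A reader might infer that deaths are not tracked or would go unreported. The documents do not support that: deaths are serious adverse events, are recorded to study completion and come before the committee by arm. What is missing is a line in the final analysis; periodic monitoring and an undertaking to analyse adverse events further do not specify one.

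A reader might also take 22.6 points as the excess to be feared here. It comes from a 45 L/min trial. This one uses 15 L/min for four hours and excludes patients planned for alteplase or endovascular therapy.

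Nor do the documents show that the mean mRS would miss a large excess. In simulations with 100 per arm, assumed control mortality of 14.6–15% and no offsetting benefit, power for a 22.6-point excess ran from 24% to 83% by the mean, depending on which scores the deaths came from, against 96% by counting deaths.

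**Conclusion.** The point holds as a low-severity omission of specification. Section 17 names no baseline-adjusted between-arm analysis for three outcomes whose baselines are collected, and reports deaths only inside an average.

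The size is modest. For NIHSS, variance falls 10 to 25% against a change score at assumed correlations of 0.8 to 0.5. For deaths, a 95% interval of about ±7 to ±10 points would be available at 100 per arm, if mortality is equal at an assumed 5 to 15%. For biomarkers the gain cannot be stated without data on skewness.

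No stated figure is shown to be wrong by this point, the feasibility conclusion does not change, and the cited deaths serve only as motivation.

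**What to change.** In Section 17, keeping these outcomes secondary or exploratory:

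1. Analyse 24-hour NIHSS by ANCOVA on baseline NIHSS, and align the Section 4 and Section 17 descriptions of the outcome. Adjust the 3-month mRS comparison for pre-stroke mRS and baseline NIHSS.
2. Report between-arm contrasts with 95% CI for MMP-9, IL-6 and IL-8 at 4 and 24 hours, adjusted for the T0 value, on the log scale (geometric mean ratios).
3. Show the full mRS distribution by arm, and deaths by 3 months by arm with a risk difference and 95% CI, stating the denominator.

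The cost is a few sentences and a little more analysis time, best settled before outcome data are examined by arm. No new patients, visits or measurements are needed.

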The primary study outcome is to determine the feasibility of enrolling and randomizing AIS patients to a therapeutic intervention within less than one hour of ED presentation. Secondary outcomes of potential therapeutic effect to inform future clinical trial(s) include penumbral salvage at repeat imaging, change in NIHSS over the first 24 hours, and 3-month mRS. To assess potential adverse effects on markers of worsening stroke severity and possible hyperoxic lung injury, levels of MMP-9, IL-6, and IL-8 will be measured at initiation, 4 hours and 24 hours. Further analysis of additional biomarkers will be considered in the future.

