4.1. SUBJECT POPULATION

Eligible subjects will include acute ischemic stroke (AIS) patients aged 18 years or older who present to the UCH ED. There will be no specific selection of subjects based on sex, race or ethnicity, age, or socioeconomic status. We anticipate the study population to be representative of that of the greater Colorado Springs and Aurora, CO area with the exception that stroke prevalence increases with age and this will likely be reflected in the final study population.

Subjects with a suspected stroke who are normoxic at baseline (room air SpO₂≥94%) and have either 1) a target mismatch lesion on CT-perfusion [defined by RAPID automated software demonstrating a ratio of PWI_{Tmax>6} lesion volume/Infarct volume (with cerebral blood flow <30% normal) greater than 1.2 or 2) a non-contrast CT-head RAPID ASPECT score of 10 (suggesting a patient has not completed their infarct), a NIHSS≥ 1, and a LKW ≤ 12 hours will be screened for eligibility. While some vulnerable populations (i.e. children and prisoners) will be excluded, AIS by the nature of the disease has the potential to impair a subject's capability to give informed consent and places them in the category of a vulnerable population. All subjects will be evaluated for the ability to give informed consent through use of the University of California, San Diego, Brief Assessment of Capacity to Consent (UABCC) Form⁵³. In cases where the subject is determined to lack the ability to provide consent, the subject's legally authorized representative (LAR) will be approached. Consent forms describing in appropriate detail the study interventions, study procedures, and risks will

be given to the participant and/or their LAR. If and when the study subject regains capacity, they will be approached for continued participation. If the subject/LAR consents for participation he/she will sign the informed consent form prior to any study procedures being done.

In terms of potential pregnant women, it is anticipated that most women will be older than likely childbearing age. While supplemental oxygen use in pregnant women experiencing fetal distress is routine, the effects of maternal hyperoxia on a developing fetus are unknown. Those of likely childbearing potential will be excluded. If a subject withdraws for any reason from the study, he/she will be replaced to meet the enrollment goal when possible. Our target enrollment will be 200 patients (~100 per arm).

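### The exploratory biomarker analysis stops at the raw mean and SD of change; a log-scale, baseline-adjusted comparison of arms with a confidence interval would answer the question better at no cost

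*Combined protocol and SAP*

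**What the plan says.** Section 4 (Study Design) gives the purpose of the markers: "To assess potential adverse effects on markers of worsening stroke severity and possible hyperoxic lung injury". The same sentence sets the sampling times: "levels of MMP-9, IL-6, and IL-8 will be measured at initiation, 4 hours and 24 hours". The hypothesis earlier in Section 4 includes the expectation that hyperoxia will not raise markers tied to reperfusion injury or to hyperoxic lung injury.

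Section 17 (Data Analysis Plan) calls this "an exploratory analysis of the effects of hyperoxia on biomarkers of stroke severity and hyperoxic lung injury will be evaluated over time". The method follows in one sentence. Its subject is "The change in level of biomarkers (MMP-9, IL-6, and IL-8) over time", and all that it says of the method is that this quantity "will be analyzed and reported using the mean and standard deviation and will be depicted graphically". Earlier in the section the plan states: "This study is not powered to detect significant differences in secondary or exploratory outcomes".

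For the markers, Section 17 gives no transformation, median or geometric mean, no rule for values outside the assay range, no model and no between-arm estimate with an interval. It also does not define the change: absolute or ratio, to 4 h or to 24 h, within subject or between visit means.

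**The concern.** Concentration markers cannot be negative and may have a long upper tail. If these do, the raw mean and SD of change are driven by a handful of subjects and describe the rest poorly. Simple change is also a less efficient use of the baseline sample than adjusting for it in a model.

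At stake is the hypothesis clause on injury markers. Two sets of means and SDs, with no contrast between arms and no interval, neither support nor refute it. A reader who sees similar-looking graphs could take them as evidence of no increase when the data were too noisy to show one. Section 2 says that the results will inform a later trial, so that reading could carry forward.

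**Working it through.** **No figure to reproduce.** The documents give no power, SD, effect size or distribution for any biomarker. Everything below on the markers is illustrative.

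**Inputs**
- From the documents: 1:1 allocation and about 100 per arm (Sections 7 and 4.1); samples at initiation, 4 h and 24 h (Section 4).
- Assumed: lognormal markers, log-SD 0.5 to 1.2, log-scale correlation r between baseline and follow-up of 0.5 to 0.7, true follow-up ratio 1.5, two-sided alpha 0.05.
- Assumed: 80 per arm. This is 100 less the 20% loss that Section 17 allows for follow-up imaging. It fits the imaging figure there: 41 × √(2/80) × (1.960 + 0.842) = 18.2, against the stated 18. No loss is stated for blood samples.

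**Step 1: influence of extreme values.** This is the share of the sum of squares of raw change that comes from the 5 most extreme of 100 subjects (simulated, r from 0.3 to 0.7). Normal data give about 28%.

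| log-SD | share from 5 of 100 |
|---|---|
| 0.5 | 39-41% |
| 0.8 | 52-55% |
| 1.0 | 61-64% |
| 1.2 | 69-73% |

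**Step 2: change versus baseline adjustment, both on the log scale.** Relative to the follow-up variance, simple change has variance 2(1 − r) and ANCOVA has 1 − r².

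| r | change | ANCOVA |
|---|---|---|
| 0.3 | 1.40 | 0.91 |
| 0.5 | 1.00 | 0.75 |
| 0.7 | 0.60 | 0.51 |

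**Step 3: power (simulated, 80 per arm, ratio 1.5, r from 0.5 to 0.7)**

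| log-SD | t-test on raw change | log ANCOVA |
|---|---|---|
| 0.5 | about 100% | about 100% |
| 0.8 | 79-94% | 96-100% |
| 1.0 | 51-67% | 83-95% |
| 1.2 | 31-43% | 68-83% |

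Repeated simulations agree within about three percentage points.

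A hand check of the ANCOVA column at log-SD 1.0 uses ln 1.5 = 0.405 and SE = √((1 − r²) × 2/80). At r = 0.5, SE = 0.137 and power is Φ(0.405/0.137 − 1.96) ≈ 84%. At r = 0.7, SE = 0.113 and power ≈ 95%.

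**Step 4: where the gain comes from (log-SD 1.0).** At r = 0.5, raw change, log change and log ANCOVA give about 50%, 71% and 82%. At r = 0.7 they give 68%, 92% and 95%. Over this range most of the gain is the log scale, and baseline adjustment adds the rest.

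**Step 5: sensitivity.** With 100 per arm, ratio 1.4 and r from 0.3 to 0.7, raw change against log ANCOVA gives 97-100% against about 100% (log-SD 0.5), 59-89% against 88-99% (0.8), 37-61% against 70-91% (1.0) and 22-40% against 53-78% (1.2). At r = 0.3 and log-SD 1.0 the three methods give 37%, 52% and 70%, so with a weak correlation baseline adjustment contributes about as much as the log scale.

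**Step 6: what an interval would show.** At log-SD 1.0, r = 0.5 and 80 per arm, an observed ratio of 1.0 has a 95% CI of exp(±1.96 × 0.137), or 0.76 to 1.31. That tells the reader how large an increase remains compatible with the data; a mean and SD per arm do not state it.

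**The case against.** The strongest reply is that this is a descriptive, exploratory analysis in a feasibility trial that disclaims power for such outcomes. The plan names no biomarker test and no decision rule, so the raw-change power figures belong to a t-test supplied here for comparison, not to the plan. That stands, and it limits the severity. It does not remove the point: lack of power is a reason to use an efficient estimate and show its interval.

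The skewness, log-SDs, correlation, effect ratio and 80 per arm are all assumptions. That also stands. With mild skew (log-SD 0.5) the power difference disappears, partly because either method detects an effect of this size.

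Two stronger readings are tempting, and the documents support neither:
- A reader might infer that the plan ignores each subject's baseline. The sentence concerns the change in level, and a sample is taken at initiation, so on the natural reading baseline is subtracted. What is missing is a definition of the change and a model that adjusts for baseline.
- A reader might infer that the markers are the trial's only safeguard against lung or brain harm. Section 16 follows respiratory compromise at 4 h, 24 h and 3 months, as well as hemorrhagic conversion and solicited adverse events, under a safety committee that meets at least twice a year.

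Finally, the plan's reference to effects of hyperoxia on the markers implies that arms will be compared. It does not say by what estimate.

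**Conclusion.** The point holds as a minor, free improvement. What the documents establish is the gap: an undefined change, summarised by raw mean and SD, with no skew-robust summary, baseline-adjusted model or between-arm interval, for the only named measure of one clause of the hypothesis.

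The size of the loss is conditional. Under the lognormal assumptions with 80 per arm and a ratio of 1.5, it runs from nothing at log-SD 0.5 to about 40 percentage points of power at log-SD 1.2 (31-43% against 68-83%). Log ANCOVA was not worse than raw change in any setting examined, but every setting assumed a multiplicative effect on a lognormal marker. The figures illustrate relative efficiency; they are not a forecast for this trial.

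**What to change.** Replace the biomarker sentence in Section 17 with a short specification:
- Log-transform MMP-9, IL-6 and IL-8, and state how values outside the assay range are handled.
- Compare arms at 4 h and at 24 h by ANCOVA, or by a repeated-measures model, with the log baseline value as covariate.
- Report the geometric mean ratio between arms with its 95% CI at each time, and read any statement of no increase from the upper limit.
- Give medians and IQRs by arm and time descriptively, and keep the graphs.
- Keep the analysis labelled exploratory.

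The cost is wording only. Serum is already scheduled at all three times (Table 1), and Section 3 has the assays run together after recruitment ends, so the method can be fixed before any biomarker result exists. No extra patients, samples or visits are needed.
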